#### 4.8.2 Schedule

This trial will use the same vaccination schedule used in RV144, in HVTN 097 (which is administering the RV144 vaccine regimen in a South African study population), and the primary vaccine regimen in the HVTN 100 trial, which will administer the ALVAC-HIV (vCP2438) + Bivalent Subtype C gp120/MF59® vaccine regimen in South Africa.

Considerations underlying selection of this schedule for RV144 are described in Section 4.11.4.1.

Furthermore, in light of the lower IgA responses seen in HVTN 096 when recombinant NYVAC and AIDSVAX B/E were co-administered at all time points, we will also evaluate the concurrent administration of ALVAC-HIV (vCP2438) + Bivalent Subtype C gp120/MF59® in a separate group. This latter schedule will administer the vaccines at months 0, 1, and 6 to determine if longer interval of the third boost will allow a maturation of antibody responses as seen for influenza vaccines [34]. In addition, data from HVTN 096 shows that antibody responses peaked after the third protein administration in the groups with protein co-administered at every vaccination.

#### **4.8.3 Prime-boost regimen**

In Groups 1, 2, and 4, this trial will employ the same strategy as RV144, that is, utilizing the ALVAC vector as a prime and the ALVAC vector/protein dual component boost. Group 3 participants will receive the ALVAC vector/protein dual component concurrently at Months 0, 1, 6, and 12. The HIV Env inserts in the ALVAC vector differ from those in RV144 in that they encode subtype C Env to more closely match the viral strains present in the Southern Africa region [41-44]. As noted above, ALVAC-HIV (vCP2438) encodes the subtype C Env gp120 from HIV-1 strain 96ZM651 in addition to the same Gag and parts of Pol used in RV144 (HIV-1 clade B LAI strain). The Bivalent Subtype C gp120 protein consists of two subtype C recombinant monomeric proteins, TV1.C gp120 and 1086.C gp120.

#### **4.8.4 Choice of control**

The vaccine regimen with the unadjuvanted Bivalent subtype C gp120 protein will serve as an active control for the two regimens containing MF59® and alum adjuvants.

#### **4.8.5 Rationale for the innate, early adaptive and mucosal sampling timepoints**

Examining the effects that the two adjuvants have on a variety of immune responses relative to each other and to the unadjuvanted protein is an important goal of this study.

Systemic innate immune responses will be measured on Day 1 and Day 3 following the vaccination when participants are first exposed to protein ± adjuvants. For Groups 1, 2, and 4, this represents Day 1 and Day 3 following the third vaccination. For Group 3, this sampling will take place on Day 1 and Day 3 following the first vaccination.

For Groups 1, 2, and 4, early systemic adaptive immune responses will be measured in samples collected at Day 0, Month 0.25, Month 3.25, Month 6.25, and Month 12.25. For Group 3, these samples will be collected at Day 0, Month 0.25, Month 6.25, and Month 12.25. These samples will provide both baseline and postvaccine information.

Systemic and mucosal samples collected at Day 0 provide the baseline values prior to vaccination while those collected at Month 6.5 provide data on peak vaccine-induced mucosal and systemic adaptive immune responses.

Finally, collection at Month 18 will provide the opportunity to assess the durability of mucosal and systemic humoral immune responses 6 months after the last vaccination.

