## 4.8 Trial design rationale

The primary objective of the study is to compare the humoral immune responses induced by the MF59®- and alum-adjuvanted vaccine regimens; while the unadjuvanted group is included to provide information about the added value of the adjuvants. Therefore, a smaller sample size for the unadjuvanted controls is sufficient. Other important questions to be answered in this study are to compare the quality, magnitude, kinetics, and duration of the humoral and T-cell responses depending on the adjuvant used or whether ALVAC and proteins are co-administered during early vaccinations. The subset of participants who will provide innate immunity and mucosal samples will include 18 participants from each of the vaccine regimens.

Group assignments are randomized to provide unbiased estimates of the safety and immunogenicity parameters of the different study arms. In addition, Groups 1, 2, and 4 are double blinded to study arm assignment. Because Group 3 has a different vaccination schedule and because blood draws for innate immunity assays occur at different timepoints from the other 3 groups in the trial, it would not be possible to include Group 3 in the blind without imposing an excessive number of unnecessary clinic visits, placebo injections, and (possibly) invasive study procedures on all trial participants. For this reason, a decision was taken to not include Group 3 in the blind.

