For quantitative assay data (eg, level of vaccine-induced IgG Ab binding to the 2 gp120 Env proteins contained in the vaccine regimen), graphical and tabular summaries of the distributions by antigen, treatment arm, and timepoint will be made. The difference between arms at a specific timepoint will be tested with a nonparametric Wilcoxon rank sum test if the data are not normally distributed and with a 2-sample t-test if the data appear to be normally distributed. To test for differences among the 4 vaccine arms, first a Kruskal-Wallis rank test or an F-test (depending on the normality assumption) will be used to test for overall differences. Secondly, if the overall test is significant at the 2-sided 0.05 level, then individual tests comparing the 3 pairs of vaccine arms will be done unless pre-specified. If rank-based tests are used then the tests will be inverted to construct Hodges-Lehmann point-estimates and 2-sided  $(1 - 0.05/3) \times 100\%$  CIs about the differences in location centers of the 3 pair-wise comparisons of vaccine arms. An appropriate data transformation (eg,  $\log_{10}$  transformation) may be applied to better satisfy assumptions of symmetry and homoscedasticity (constant variance).

Some immunologic assays have underlying continuous or count-type readout that are dichotomized into responder/nonresponder categories (eg, binding antibody multiplex assay [BAMA]). If treatment arm differences for these assays are best summarized by a mixture model, then Lachenbruch's test statistic [71] will be used to evaluate the composite null hypothesis of equal response rates in the MF59® vs aluminum hydroxide adjuvanted arms and equal response distributions among responders in the 2 arms. This test statistic equals the square of a binomial Z-statistic for comparing the response rates plus the square of a Wilcoxon statistic for comparing the response distributions in the subgroup of responders. A permutation procedure is used to obtain a 2-sided p-value. For estimation, differences in response rates between arms will be estimated using the methods described above, and in the subgroup of positive responders, differences in location parameters between arms will be estimated using the methods described above.

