## 9.5 Innate immunity and mucosal sampling

Innate immunity samples and mucosal samples will be collected at the timepoints indicated in Appendix G, Appendix I, Appendix K, and Appendix M from the subset of study participants who agree to these procedures.

Participants who consent to provide cervical, rectal, or semen samples will be tested for the following infections at the mucosal sampling visits: gonorrhea, chlamydia, and syphilis. Participants who consent to provide cervical fluid samples will be tested for trichomoniasis and for bacterial vaginosis and (if clinically indicated) for hyphae/budding yeast. Test results will be provided to participants and all participants who test positive for 1 or more of these infections will receive counseling as well as treatment or referral for treatment as appropriate. Sample collection may not be performed or may be deferred to a later date within the visit window if a contraindication to sampling (eg, active GTI) is present (as indicated below).

**Rectal fluid sampling (both sexes):** For participants born female, a pregnancy test must be performed and be negative prior to any rectal mucosal sampling. Persons who are NOT of reproductive potential due to having undergone total hysterectomy or bilateral oophorectomy (verified by medical records), are not required to undergo pregnancy testing. Rectal secretion sampling should be deferred if a participant is menstruating, but should be performed as soon as possible, if still within the visit window. In addition, rectal sampling will not be performed (or may be deferred to a later date if still within the

visit window) if there is a contraindication to rectal secretion sampling, such as an active infection or inflammation of the colorectal area (such as an herpes simplex virus (HSV)-2 outbreak or inflamed hemorrhoids or colitis/diarrhea) or if the participant has any active genital tract infection (GTI).

For 48 hours prior to sample collection, participants should abstain from:

- Receptive anal sex,
- Insertion of any foreign object or substance into the anus (including but not limited to cleaning products [creams, gels, lotions, pads, etc.], lubricant, enemas, and douching even with water), and
- Using perianal or intra-anal steroid or other anti-inflammatory cream in or around the anus.

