## Appendix F Laboratory procedures (Groups 1, 2, and 4)

Visit: Day: Weeks: Month:	1	2	3	4	5	6	7	8	9	10	11	12	13	14	15	16	17	18	19	20	21	
	D0	D1	D3	D7	D28	D42	D84	D85	D87	D91	D98	D168	D175	D182	D273	D364	D371	D378	D455	D546		
	W0			W1	W4	W6	W12			W13	W14	W24	W25	W26	W39	W52	W53	W54	W60	W72		
	M0			M0.25	M1	M1.5	M3			M3.25	M3.5	M6	M6.25	M6.5	M9	M12	M12.25	M12.5	M15	M18		
Ship to 	Assay location 	Tube Type 	Tube size (vol. capacity) 					ALVAC				ALVAC+prot+MF59 OR Alum OR No Adj				ALVAC+prot+MF59 OR Alum OR No Adj						
BLOOD COLLECTION																					Total	
Screening/Diagnostic																						
Screening HIV test	Local lab	Local lab	EDTA	2mL	4	—	—	—	—	—	—	—	—	—	—	—	—	—	—	—	4	
HBSAg/anti-HCV	Local lab	Local lab	SST	5mL	5																5	
HIV diagnostics 	HSML-NICD	HSML-NICD	EDTA	10mL							10				10		10	10	10	10	70	
STI Serology																						
Syphilis	Local lab	Local lab	SST	5mL	5	—	—	—	—	—	—	—	—	—	—	—	—	—	—	—	5	
Safety labs																						
GBC/Diff/ platelets	Local lab	Local lab	EDTA	5mL	5	—	—	5	—	5	—	—	—	—	6	—	5	—	5	5	35	
Chemistry panel 	Local lab	Local lab	SST	5mL	5	—	—	5	—	5	—	—	—	5	—	5	—	5	5	5	35	
Immunogenicity & Virologic assays																						
HLA host genetics 	BARC	HVTN Labs	ACD	8.5mL	—	17	—	—	—	—	—	—	—	—	—	—	—	—	—	—	17	
Cellular assays																						
ICS	BARC	HVTN Labs	ACD	8.5mL	—	85	—	—	—	85	—	—	—	85	—	85	—	85	—	85	595	
Phenotyping (pT11 and plasmablasts)	BARC	HVTN Labs	ACD	8.5mL	—	17	—	17	—	—	—	—	—	17	—	17	—	17	—	17	595	
Humoral assays																						
Binding Ab Assay	BARC	HVTN Labs	SST	8.5mL	—	8.5	—	—	—	8.5	—	—	—	8.5	—	8.5	8.5	8.5	—	8.5	68	
Neutralizing Ab Assay	BARC	HVTN Labs	SST	8.5mL	—	8.5	—	—	—	8.5	—	—	—	8.5	—	8.5	—	8.5	—	8.5	60	
Storage																						
PBMC	BARC		ACD	8.5mL	—	42.5	—	34	—	59.5	—	—	—	59.5	—	59.5	59.5	59.5	51	59.5	544	
Serum	BARC		SST	8.5mL	—	17	—	—	—	17	—	—	—	17	—	17	17	17	—	17	136	
Visit total					24	196	0	0	61	0	189	10	0	0	0	189	10	77	189	36	206	68
56-Day total					24	220	220	220	281	281	469	199	199	199	387	10	87	275	36	206	274	462
URINE COLLECTION																						
Urinalysis	Local lab	Local lab			X	—	—	X	—	—	—	—	—	—	—	—	—	X	—	—	—	
Pregnancy Test 	Local lab	Local lab			X	X	—	—	X	—	X	—	—	X	—	—	X	—	—	X	—	
STOOL COLLECTION (OPTIONAL)																						

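### The default between-arm test for the innate and cell-phenotype assays has no baseline term, so the pre-dose values already collected are not used for precision

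*Combined protocol and SAP*

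**What the plan says.** **Sampling.** Section 4.8.5 states: "Systemic innate immune responses will be measured on Day 1 and Day 3 following the vaccination" at which participants first meet protein. That is the third vaccination in Groups 1, 2 and 4 and the first in Group 3. The next paragraph lists the early adaptive samples, Day 0 included, and adds: "These samples will provide both baseline and postvaccine information". A later sentence reads: "Systemic and mucosal samples collected at Day 0 provide the baseline values prior to vaccination". It pairs Day 0 with the Month 6.5 peak of adaptive responses. The innate paragraph names no baseline visit.

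**Who is sampled.** Section 4.8: "The subset of participants who will provide innate immunity and mucosal samples will include 18 participants from each of the vaccine regimens". Section 9.5 takes innate and mucosal samples "from the subset of study participants who agree to these procedures". Appendices F and H, which cover participants outside that subset, also schedule pTfh/plasmablast phenotyping.

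**Analysis.** Section 6.4.4.1 says of quantitative assay data: "The difference between arms at a specific timepoint will be tested with a nonparametric Wilcoxon rank sum test" if they are not normal, and "with a 2-sample t-test if the data appear to be normally distributed". A transformation is allowed. The same section adds Lachenbruch's two-part test, GEE, likelihood-based generalized linear models and linear mixed models. The GEE and likelihood models take as covariates the baseline predictors of missing outcomes. The outcome's own pre-dose value is neither named nor excluded. Section 10.6.2 says gene-expression changes will be analysed over time but gives no between-arm test. No section is specific to innate or phenotyping data.

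**The concern.** Section 4.8.5 calls the effect of the adjuvants on a variety of immune responses an important goal. Serum cytokines and circulating cell frequencies are not zero before vaccination and differ between people. A comparison of post-dose values alone leaves that between-person variation in the error term, although participants have given blood that could remove part of it. The loss matters most where the arms are smallest, which is the MF59, alum and no-adjuvant innate contrast.

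The unstated innate baseline is a second gap. By Day 84, Groups 1, 2 and 4 have had two ALVAC doses, and their innate samples after first protein exposure fall on Days 85 and 87. Analysts who chose Day 0 or Day 84 as baseline could report different adjusted results from the same data.

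HIV-specific serum antibody should be near zero before vaccination, so the primary antibody endpoints are not affected.

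**Working it through.** **1. Are pre-dose innate samples drawn?** Yes. In Appendix G, Day 84 adds up as HIV diagnostics 10 + CBC 5 + pTfh/plasmablast phenotyping 17 + serum cytokines 8.5 + RNA 3 + innate phenotyping 8.5 = 52 mL. The stated visit total is 52, so the innate tubes must be included. Section 9.3 asks for specimen collection before vaccination. In Appendix I, the Day 0 rows for Group 3, innate tubes included, add to 166 mL, as stated.

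**2. Which comparisons have 18 per arm?** The innate assays do (4 × 18 = 72). Most pTfh/plasmablast phenotyping does not. The Appendix F totals fit only with the 17 mL phenotyping tube included:
- Day 0: 17 + 85 + 17 + 8.5 + 8.5 + 42.5 + 17 = 195.5 (stated 196)
- Day 7: 5 + 5 + 17 + 34 = 61 (stated 61)
- Day 175: 17 + 59.5 = 76.5 (stated 77)

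Phenotyping at Day 0 and Months 0.25, 6.25, 12 and 12.25 therefore covers whole arms of 36/36/36/24. Only the Day 84 and Month 3.25 draws are confined to the subset.

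**3. Evaluable numbers.** Section 6.1 plans for 15% missing at Month 6.5. If that rate applies here, 18 × 0.85 = 15.3, or about 15 per arm. Whole arms become 36 × 0.85 = 30.6 and 24 × 0.85 = 20.4.

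**4. The plan's own figures.** The plan states no power, SD or effect size for these comparisons. As a check on method, the nearest stated figures, in Table 6-4 (Fisher, 30 per arm), reproduce: 78.7% to 81.3% for the 80% column and 89.2% to 91.4% for the 90% column.

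**5. Size of the gain.** Two-sample t-test, two-sided alpha 0.05, noncentral t with df = n1 + n2 − 2 and noncentrality d / √[v(1/n1 + 1/n2)]. The variance factor v is 1 for post-dose only, 1 − ρ² for ANCOVA and 2(1 − ρ) for change from baseline. The pre/post correlation ρ is assumed.

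With 15 per arm:

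| Assumed ρ | Detectable SD, post-only | ANCOVA | Change score | Power at 0.8 SD, post-only | ANCOVA | ANCOVA acts like n = 15/(1 − ρ²) |
|---|---|---|---|---|---|---|
| 0.3 | 1.06 | 1.01 | 1.25 | 56% | 60% | 16.5 |
| 0.5 | 1.06 | 0.92 | 1.06 | 56% | 69% | 20 |
| 0.7 | 1.06 | 0.76 | 0.82 | 56% | 84% | 29 |

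The formula does not charge ANCOVA for estimating the covariate slope. A simulation that does gives about 58–59%, 67% and 83% power at 0.8 SD, so most of the gain remains.

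With all 18 per arm evaluable, 0.96 SD falls to 0.92, 0.83 and 0.69.

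**6. Whole-arm phenotyping.** The unadjusted detectable difference is 0.67 SD at 36 vs 36 and 0.75 SD at 36 vs 24, or 0.74 SD at 30 vs 30 after missing data. ANCOVA shrinks each by the same factors, 0.954, 0.866 and 0.714. At 30 vs 30 this gives 0.70, 0.64 and 0.53 SD.

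**The case against.** The strongest reply is that nothing here is invalid. An unadjusted comparison of randomised arms is unbiased, Section 5.3 makes these assays exploratory and optional, and Section 6.4.1 limits the analysis variables to primary and secondary objectives. Leaving exploratory models open is common at this stage. All of this stands, and it limits the point to efficiency and prespecification.

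Some stronger readings are tempting, but the documents do not support them:

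- **That baseline is ignored throughout, or only raw values are tested.** Section 6.4.4.1 permits transformation and names GEE, generalized linear and mixed models with baseline covariates. Those covariates are chosen for missingness, and nothing commits the analyst to the pre-dose assay value, but nothing excludes it.
- **That all these comparisons rest on 18 per arm.** This is true of the innate assays and two phenotyping draws. The sentence about baseline and postvaccine information describes the early adaptive samples, most of which are taken from whole arms.
- **That the protocol wrongly names Day 0 as the innate baseline in Groups 1, 2 and 4.** It names none. The Day 0 sentence concerns the Month 6.5 adaptive and mucosal responses.
- **That adjustment would rescue an underpowered comparison.** At ρ = 0.3 the gain is small, and even at 0.5 the detectable difference is still 0.92 SD. The wide margin comes mainly from the sample size.

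**Conclusion.** The point holds as a low-cost efficiency improvement for exploratory endpoints. The default test has no baseline term, no other passage commits to adjusting for the pre-dose assay value, and the innate baseline visit is unstated. Bias, the type I error rate and the primary analyses are not affected.

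For the 18-per-arm comparisons, with about 15 evaluable, ANCOVA would lower the detectable difference from 1.06 SD to between 1.01 and 0.76 SD over ρ from 0.3 to 0.7. This rests on two assumptions: a pre/post correlation that the documents do not give, and a 15% missing rate that they state for Month 6.5 and not for Days 85 and 87. For most phenotyping timepoints the same proportional gain applies from a better starting point of about 0.67 to 0.75 SD before missing data.

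**What to change.** **Section 6.4.4.1.** State that innate soluble factors and leukocyte, pTfh and plasmablast frequencies are compared between arms by ANCOVA on the log value (rank ANCOVA if non-normal), with the log pre-dose value as covariate:
- Visit 8 (Day 84) for the post-third-vaccination samples of the Group 1, 2 and 4 subset
- Visit 2 (Day 0) for the Group 3 samples after the first vaccination
- for other phenotyping timepoints, the closest available pre-dose draw, which is Day 0 where no later one exists

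Do not use a change score, which is less precise than the post-dose value alone when ρ is below 0.5. Keep the unadjusted Wilcoxon or t-test as a sensitivity analysis.

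**Section 4.8.5.** Name the innate baseline visit: Day 84 for Groups 1, 2 and 4, and Day 0 for Group 3.

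**Two points for the wording.** Groups 1, 2 and 4 receive the same product up to Day 84, so that value is a clean covariate among them. It is not like for like with Day 0 in Group 3, and innate contrasts with Group 3 should say so. At Month 12.25 the closest pre-dose draw is Month 12, after arm-specific doses. Adjusting for it describes the response to the last dose given the level before it. If the whole-regimen difference is wanted, Day 0 is the covariate.

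**Cost.** Plan wording and slightly more analysis, with no new visits or samples. Participants without a pre-dose value need simple imputation or drop out of the adjusted test.

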## 4.9 Plans for future product development and testing

The adjuvants used in this study (MF59® and aluminum hydroxide) have never been compared directly in a clinical trial. It is anticipated that the vaccine regimen given with MF59® will induce a systemic and mucosal Ab response of greater magnitude than the same vaccine regimen given with aluminum hydroxide and that both will surpass the magnitude of immune responses elicited by the unadjuvanted study products. Such a finding would strengthen the rationale for the planned efficacy trials in Southern Africa that will use MF59®. Moreover, the design of future vaccine studies could be adjusted if lower IgA responses are demonstrated in the vaccinees receiving the simultaneous administration of the ALVAC-HIV vector and protein combination at all timepoints compared to individuals receiving initial ALVAC-HIV prime followed by ALVAC-HIV plus protein boost, provided that coadministration at all timepoints is associated with other potentially favorable immune responses, such as high V1V2 binding antibody titers. Future vaccine design could also be impacted if a longer dosing interval allows for improved antibody maturation. If we see that mucosal Ab responses are enhanced in the aluminum hydroxide group (similar to the results observed in the previously cited NHP studies), these data can be used in conjunction with data from other planned studies to better understand immune correlates of HIV risk and to inform improvements in future vaccines and vaccine trial designs.

## 4.10 Preclinical safety studies

### 4.10.1 IM local tolerability and systemic toxicity study in New Zealand White Rabbits (Study AB20670)

An objective of the study was to determine the local tolerability and systemic toxicity of ALVAC-HIV (vCP2438)/ALVAC-HIV (vCP2438) with gp120+MF59 vaccines administered by the IM route to New Zealand White Rabbits 7 times at 2-week intervals, followed by a 2-week recovery period.

There were no deaths during the study. No treatment-related clinical signs were reported during the study and treatment was locally well tolerated. Body temperature was slightly increased, mostly after the 1st injection, but returned to normal within 48 hours. There were no effects of treatment on body weight or food consumption. No treatment-related ophthalmological findings were observed at the end of the treatment period.

When compared to the control group, a transient increase in C-reactive protein, globulin, fibrinogen, or neutrophil count was observed after one or more of the immunizations. These effects correlated with the inflammatory findings observed histopathologically at the injection sites. There were no other treatment-related differences from the controls amongst the biochemistry or hematological parameters.

At necropsy, at the end of treatment, the only histologic changes due to the test items were in the injection sites and iliolumbar and sacral lymph nodes. In the sites injected with ALVAC or gp120s+MF59, the changes comprised inflammatory cell infiltrates, necrosis, fibrosis, hemorrhage, acellular material, and mineralization. These findings were often only minimal or slight. In the lymph nodes that drained the injected sites, there was minimal or slight increased lymphoid follicle development, increased paracortex, and granulocyte infiltrate. There was evidence of partial resolution of the

described changes at both injection site and lymph nodes, based on necropsy observations after the recovery period.

In conclusion, under the defined study conditions, 7 intramuscular administrations of ALVAC-HIV (vCP2438) vaccine associated with gp120s/MF59 (last 4 injections) to the New Zealand White Rabbit at two-week intervals were clinically and locally well tolerated. The study supports the use of this vaccine regimen in human clinical trials.

